**Sponsor or funding source: NIH**

## **Background, Rationale and Context**

[figure not shown]
Oxytocin (OXT) uniformly produces antinociception and anti-hyperalgesia in rodents, yet intranasal OXT fails to reduce pain in 6 of 13 clinical studies [2]. Three observations from our group suggest that OXT is not analgesic in the normal condition, but speeds recovery from pain after injury and prevents the transition from acute to chronic pain: **1)** The incidence of chronic pain from surgery is considerably lower after cesarean section compared to other pelvic surgeries [3], **2)** recovery from hypersensitivity after nerve injury is quicker in female rats when injury occurs at the time of delivery, an effect temporarily reversed with a nonselective OXT and vasopressin 1a (V1a) receptor antagonist [4], and **3)** selective antagonists of these receptors temporarily reverse recovery from nerve injury in both male and female rodents [5].

OXT itself is the sole readily-available tool to test clinical relevance of basic science studies of OXTergic signaling in other neurologic disorders, including pain, neuroprotection during brain ischemia, ADHD and autism and in psychiatry, including social behaviors which are positive (trust, neonatal-maternal and adult pair bonding) and negative (aggression and ethnocentrism). Existing clinical studies rely primarily on correlations between disease activity and common polymorphisms in OXT receptors or plasma OXT concentrations, which are unlikely to reflect OXT release in the brain.

Direct evaluation of peripheral and central effects of systemically administered OXT in humans is hampered by bolus dosing, lack of dose response, and ignorance of peripheral and central drug distribution, especially with intranasal administration. Poor rigor and fundamental ignorance of drug disposition partly underlie the uncertainty regarding OXT's actions in acute and chronic pain.

Prior to 2016, and to a considerable extent since, OXT was and is measured with antibody-based methods (EIA, ELISA, or RIA). Reported concentrations vary widely from study to study and, since development of accurate LC/MS assays, there is now considerable skepticism regarding the validity of the previous research and concerns that the older methods measure OXT degradation fragments (see [6] for review). Note in **Figure 1** the high baseline and wide variability in OXT concentrations and markedly different change in OXT concentrations after intranasal (i.n.) administration when ELISA and RIA methods are used compared to that of LC/MS, which unambiguously measures OXT [4; 5; 8; 9].

In preliminary data we infused OXT, 17  $\mu$ g, iv in 11 healthy men and women aged 22-58 years, measured plasma OXT with both LC/MS and with ELISA using validated protocols, and modeled the resultant data using NONMEM. Transient headache and facial flushing occurred when this dose was injected over 1 min in the first 3 individuals and these effects were reduced or eliminated with infusion over 10 min in the remainder of the subjects. PK analysis showed no effect of sex and a minor effect of body weight. Modeled data from the LC/MS analysis differ significantly from those using RIA assays after iv OXT injection [2; 7], which themselves differ widely (**Figure 2A**). In our study, ELISA assays showed more inter-individual variability (NONMEM estimates of variance due to assay for ELISA was 28% compared to 16% for LC/MS) and considerably different PK parameters than those obtained from LC/MS assays. Simulated target controlled infusions (TCI) based on

**Figure 1.** Mean plasma OXT via i.n. administration by various assays.

these models demonstrate the greater variability with ELISA than LC/MS (**Figure 2B**). At the same total dose of 17  $\mu$ g OXT, a 30 min TCI infusion using PK parameters using LC/MS assays would result in a targeted concentration nearly double that using PK from ELISA assays (80 vs 46 pg/ml for LC/MS vs ELISA).

Defining PK of OXT in plasma after peripheral administration is required in order to determine PK / pharmacodynamic (PK/PD) relationships for actions centrally, the primary focus for much of neuroscience OXT research, and peripherally, the focus of our primary hypothesis regarding analgesic and disease-modifying effects of OXT in pain after injury. This requires measuring OXT with a reliable, sensitive, and specific assay to define PK and using the knowledge of PK to design dosing schemes with reliable measures of drug action at sites of interest. It also requires creation of outcome measures in the periphery (beyond those peculiar to obstetrics) and centrally which can be repeatedly measured at frequent intervals adequate for PK/PD modeling. These are the goals of this clinical project within a multi-project NIH proposal (P01-NS119159).

i.n. administration is far more practical for subacute and chronic treatment, as would be needed in clinical trials, and the purpose of the current study is to determine the bioavailability and PK of OXT after i.n. administration. The proposed study utilizes a multi-visit, crossover design. In order to determine bioavailability, each subject will receive OXT by intravenous injection on one occasion and i.n. on others. To determine linearity of OXT bioavailability across doses to be subsequently studied, two i.n. OXT doses will be administered on different occasions. Subjects will be stratified across three age groups from young adults to the elderly, with balanced recruitment by sex in order to assess covariates of age and sex in OXT PK.

## Objectives

**Main objective** Model OXT concentrations in plasma after intravenous and i.n. administration in order to determine absorption rate and bioavailability of OXT in plasma after i.n. administration.

## Additional Objectives

[figure not shown]
1. Describe adverse events with intravenous and i.n. administration

## Methods and Measures

Equal numbers of adult men and women will be recruited. Sample size will be divided into 3 groups; young (18-39-year-old) middle (40 – 59-year-old) and older (60 – 75-year-old).

Subjects will report to the CTSI Clinical Research Unit (CRU) for two visits, separated by at least 5 days. On study visit one informed consent will be obtained and eligibility verified. Then two intravenous (IV) catheters will be inserted, one in each forearm, with one for drug infusion and the other for blood sampling. After baseline measures, subjects will receive oxytocin (Pitocin®), 14  $\mu$ g (8.2 IU) over 30 minutes. This dose and infusion duration were chosen based on previous studies showing no adverse events in 10 volunteers and our preliminary PK model which predicts that plasma oxytocin concentrations will be above the limit of detection (1 pg/ml) at 120 min. Venous blood samples (5 ml) will be obtained at 2, 5, 10, 20, 30, 40, 50, 65, 90, and 120 minutes after the initiation of oxytocin administration for oxytocin assay.

On study visit 2, one IV catheter will be placed for blood sampling. After baseline measures, subjects will receive 102  $\mu$ g (60 IU) intranasal oxytocin (Tonix-1900, Tonix Pharmaceuticals, Chatham, NJ). Venous blood samples (5 ml) will be obtained at 1, 2, 5, 7, 10, 15, 20, 25, 35, 45, and 60 minutes after the initiation of the oxytocin administration for oxytocin assay. See graph 3 for rationale for the times of sampling.

**Figure 2. A)** PK modeled OXT concentrations in preliminary data compared with published reports. **B)** Fraction of targeted concentration using TCI. 95% prediction intervals from LC/MS or ELISA assays of duplicate samples (n=11).

We will abandon an individual participant's study and schedule another participant should we be unable to successfully place the intravenous catheters.

## **STUDY DESIGN**

This is a sequential study of subjects, all of whom will receive, on different occasions, an intravenous infusion or intranasal (i.n.) sprays of oxytocin. Blood samples will be obtained thereafter in order to create a mathematical model to describe the concentrations of oxytocin in the blood over time (pharmacokinetics). In this study, healthy volunteers are recruited for two study drug visits. They will come to the CRU and have two IV catheters inserted, one in each arm for the first study visit. They will receive a 30 minute infusion through one of the IV catheters of oxytocin, 14  $\mu$ g, and blood will be obtained at several times over the next 120 minutes and the amount of oxytocin measured in the blood samples. They will come a second time to the CRU and have one IV inserted in their arm and self-administer i.n. oxytocin, 102 ug over 5 min and blood will be obtained several times over the next 60 minutes and the amount of oxytocin measured in the blood samples. Plasma oxytocin concentrations and individual subject characteristics (age, sex, weight, height, race, and ethnicity) will be analyzed by another group at Stanford University funded under the same NIH grant supporting the work at Wake Forest. The effect of these subject characteristics on the pharmacokinetics of oxytocin will be examined, since these characteristics alter concentration over time of some drugs. Should these characteristics alter oxytocin concentrations, we and others could adjust the dose of oxytocin to the individual.

The main purpose of this study is to sample blood and calculate the pharmacokinetics of oxytocin. We will also assess adverse events during the study.

The research participants will not benefit from this study, but the knowledge we get will be important not only to adjust oxytocin dose to individuals, but to study its possible effects on pain in a more precise way by controlling the amount of oxytocin in the blood circulation. The sample size we chose is needed to get an accurate estimate for the parameters in the pharmacokinetic model for the population in general, not just the subjects in this study.

## **Setting**

[figure not shown]
Study visits will occur on the main campus at Atrium Wake Forest Baptist Health in the Clinical Research Unit (CRU).

## **Subjects selection criteria**

The study will enroll healthy subjects.

### **Inclusion Criteria**

1. Male or female  $\geq$  18 and  $<$  75 years of age, Body Mass Index (BMI)  $<40$ .
2. Generally in good health as determined by the Principal Investigator based on prior medical history, American Society of Anesthesiologists physical status 1 or 2.
3. For healthy volunteers, normal blood pressure (systolic 100-140 mmHg; diastolic 60-90 mmHg) resting heart rate 45-90 beats per minute) without medication. For those with hypertension, blood pressure controlled with anti-hypertensive medication and with a resting heart rate 45-100 beats per minute.

**Figure 3. Simulated PK and blood sampling times**

**A)** Simulated plasma OXT concentrations (Cp) with IV infusion. The proposed sampling times (red circles) optimize the informational content to confirm the model generated from 11 subjects in an earlier study.

**B)** Simulated plasma OXT concentrations (Cp) with I.N. self-administration. The proposed sampling times (red circles) optimize the informational content to capture the absorption rate constant. The simulated model assumed a Cmax of 15 min and 1% bioavailability.

The effect of these subject characteristics on the pharmacokinetics of oxytocin will be examined, since these characteristics alter concentration over time of some drugs. Should these characteristics alter oxytocin concentrations, we and others could adjust the dose of oxytocin to the individual.

The main purpose of this study is to sample blood and calculate the pharmacokinetics of oxytocin. We will also assess adverse events during the study.

The research participants will not benefit from this study, but the knowledge we get will be important not only to adjust oxytocin dose to individuals, but to study its possible effects on pain in a more precise way by controlling the amount of oxytocin in the blood circulation. The sample size we chose is needed to get an accurate estimate for the parameters in the pharmacokinetic model for the population in general, not just the subjects in this study.

## **Setting**

Study visits will occur on the main campus at Atrium Wake Forest Baptist Health in the Clinical Research Unit (CRU).

## **Subjects selection criteria**

The study will enroll healthy subjects.

### **Inclusion Criteria**

1. Male or female  $\geq$  18 and  $<$  75 years of age, Body Mass Index (BMI)  $<40$ .
2. Generally in good health as determined by the Principal Investigator based on prior medical history, American Society of Anesthesiologists physical status 1 or 2.
3. For healthy volunteers, normal blood pressure (systolic 100-140 mmHg; diastolic 60-90 mmHg) resting heart rate 45-90 beats per minute) without medication. For those with hypertension, blood pressure controlled with anti-hypertensive medication and with a resting heart rate 45-100 beats per minute.

4. Female subjects of child-bearing potential and those < 1 year post-menopausal, must be practicing highly effective methods of birth control such as hormonal methods (e.g., combined oral, implantable, injectable, or transdermal contraceptives), double barrier methods (e.g., condoms, sponge, diaphragm, or vaginal ring plus spermicidal jellies or cream), or total abstinence from heterosexual intercourse for a minimum of 1 full cycle before study drug administration.

### **Exclusion Criteria**

1. Hypersensitivity, allergy, or significant reaction to any ingredient of Pitocin®
2. Any disease, diagnosis, or condition (medical or surgical) that, in the opinion of the Principal Investigator, would place the subject at increased risk (active gynecologic disease in which increased tone would be detrimental e.g., uterine fibroids with ongoing bleeding), compromise the subject's compliance with study procedures, or compromise the quality of the data
3. Women who are pregnant (positive result for urine pregnancy test at visit 1), women who are currently nursing or lactating, women that have been pregnant within 2 years
4. Subjects with neuropathy, chronic pain (being treated on a daily basis), diabetes mellitus, or taking benzodiazepines or pain medications on a daily basis.
5. Subjects with current or history of ventricular tachycardia, atrial fibrillation or prolonged QT interval.
6. Subjects with past or current history of hyponatremia or at risk for hyponatremia; anyone taking thiazide diuretics, loop diuretics, combination diuretics, lithium, carbamazepine, enalapril, Ramipril, celecoxib, temazepam, gliclazide, glimepiride, glibenclamide, glipizide, omeprazole, pantoprazole, desmopressin, SSRI's, MAOI, or the recreational drug ecstasy.
7. Subjects with a known latex allergy.
8. History of chronic nasal obstruction or local pathology in nostril pathway which, in the opinion of the investigator, would prevent appropriate nasal administration of the study drug.
9. Use of OTC nasal products (ie. Saline spray, Neti-Pot, etc.) or intranasal corticosteroid medications during the study.

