### **Sample Size**

We request permission to study up to 30 subjects so that we will have 24 evaluable subjects, respectively, with complete sampling at all time periods. Sample size will be divided into 3 groups; young (18-39-year-old) middle (40 – 59-year-old) and older (60 – 75-year-old).

Sample size was determined using of bootstrap analyses and conventional calculations to estimate the pharmacokinetic parameters within the desired level of accuracy. Table 1 shows the results of 1000 bootstrap replications of the original 11 individuals in the pharmacokinetic study, resampled with N = 11 (the original study size) and N = 20. As expected, the estimates are more precise with increasing study size. The mean and 95% confidence intervals are shown for each parameter.

N	Parameter	Mean	95% Confidence Bound		Range	Correction	Corrected Range
			Lower	Upper			
11	Cl1	0.98	0.89	1.08	20%	2.54	50%
	V1	10.2	8.9	11.9	29%		74%
	Cl2	0.21	0.18	0.24	29%		74%
	V2	7.1	6.1	8.1	28%		70%
20	Cl1	0.97	0.95	1.01	7%	1.88	12%
	V1	10.1	9.6	10.6	10%		18%
	Cl2	0.20	0.20	0.21	8%		16%
	V2	7.0	6.7	7.3	8%		16%

**Table 1** Bootstrap parameter estimates of PK model.

The 95% confidence intervals from the bootstrap are corrected to provide a “best” estimate of the true 95% CI using the upper confidence limit (UCL) method of Browne [1]. As described by Whitehead [10], the 95% UCL correction is  $k/\chi_{(0.95,k)}^2$  where k is N-1, the number of degrees of freedom. As seen in Table 1, the parameters estimated for the initial 11 subjects have a reasonable level of certainty (95% CI < 30% of the mean value) for a small study. However, the corrected CI range from the bootstrap for an N=11 study is closer to 70%. A study with 20 subjects will estimate the parameters within a corrected 95% CI range within 20% of the mean estimated value (Table 1, numbers in red). This is sufficient accuracy to inform the subsequent studies.

Sample size in this study is increased to 24 to permit stratifying by age (3 strata), weight (2 strata), and sex. A corrected confidence range less than 20% (Table 1) implies that mixed effect analysis will distinguish covariate effects in the range of 40% in a study with 20 or more subjects. This is the range at which the covariate effect may be clinically consequential. In practice, mixed-effects analysis with NONMEM is often sensitive to covariate effects smaller than predicted by preliminary analyses.

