## **Interventions and Interactions**

**Study Visit 1:** The participant will report to the Clinical Research Unit (CRU) of the Wake Forest Clinical Translational Science Institute (CTSI), in the morning after having had nothing to eat or drink since midnight. The participant will review and sign the Informed Consent. After informed consent is adequately obtained, a detailed medical history will be obtained from the participant, female participants will have a urine pregnancy test performed to determine pregnancy status. Vital signs to include blood pressure (BP), heart rate (HR), respiratory rate (Resp) and peripheral oxygen saturation (POX) will be measured and recorded along with height and weight.

Once eligibility has been determined; baseline vital signs (BP, HR, Resp, POX) will be obtained for a baseline measurement and then at the following intervals after the infusion has been initiated; 5, 10, 30, 60, 90 and 120 minutes. Two intravenous catheters will be inserted, one in each arm, and baseline measurements will be obtained. Then 14 µg (8.2 IU) oxytocin (Pitocin®), obtained from the research pharmacy, will be infused over 30 min through one of the catheters. Blood (5 ml) will be sampled from the other catheter at 2, 5, 10, 20, 30, 40, 50, 65, 90, and 120 minutes after the initiation of oxytocin, placed on ice, plasma separated in a refrigerated centrifuge, and stored at -80°C until analyzed for oxytocin concentration. The study will not be blinded. The intravenous catheters will be removed after all data collection and the subject discharged from the CRU. The duration for study visit 2 will be approximately 3.5 hours.

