## **Study Visit 2**

On the second visit, the participant will report to the CRU, in the morning after having had nothing to eat or drink since midnight. Baseline vital signs (BP, HR, Resp, POX) will be obtained for a baseline measurement and then at the following intervals after the intranasal oxytocin: 10, 20, 30, 60, 90 and 120 minutes. One intravenous catheter will be inserted. Oxytocin, 102 µg (Tonix-1900, Tonix Pharmaceuticals, Chatham, NJ), obtained from the research pharmacy, will be self-administered in the nasal passages as one metered spray in each nostril followed in 5 min by a second metered spray in each nostril. Blood (5 ml) will be sampled from the IV catheter at 1, 2, 5, 7, 10, 15, 20, 25, 35, 45, and 60 minutes after the initiation of the oxytocin administration, placed on ice, plasma separated in a refrigerated centrifuge, and stored at -80°C until analyzed for oxytocin concentration. The intravenous catheter will be removed after all data collection and the subject discharged from the CRU. The duration for study visit 2 will be approximately 3 hours.

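### Pregnancy is tested only before the first oxytocin dose; no test is listed before the second dose at visit 2, at least 5 days later with no maximum interval

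*Combined protocol and SAP*

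**What the plan says.** Exclusion 3 bars "Women who are pregnant (positive result for urine pregnancy test at visit 1", together with women who are nursing or were recently pregnant. The matching procedure appears once, under Interventions and Interactions for Study Visit 1: after consent, "female participants will have a urine pregnancy test performed to determine pregnancy status". Methods and Measures places the eligibility check at the same visit: "On study visit one informed consent will be obtained and eligibility verified".

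Methods and Measures brings subjects in "for two visits, separated by at least 5 days". That sets a minimum gap, and no section sets a maximum.

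Study Visit 2 begins with a fasting arrival and baseline vital signs, which are repeated "then at the following intervals after the intranasal oxytocin" at listed times. One catheter is placed and the subject self-administers 102 µg of oxytocin. No pregnancy test and no renewed eligibility check is listed.

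Inclusion 4 requires women of child-bearing potential, and those less than a year past menopause, to use highly effective contraception or abstain, "for a minimum of 1 full cycle before study drug administration".

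**The concern.** Each subject receives oxytocin twice, but pregnancy status is tested only before the first dose. The plan regards pregnancy as a reason not to give the drug, and before visit 1 it does not rely on contraception or self-report: it tests. The same reasoning applies before visit 2, where the visit 1 result is at least 5 days old and, as written, never expires.

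At stake is one avoidable event: a woman with an unrecognised pregnancy receives the intranasal dose that the exclusion is meant to keep from her. The Study Design section says participants gain no benefit from the study, so nothing offsets that exposure. The statistical analysis is not affected.

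**Working it through.** The plan states no figure to reproduce. The check has two parts: whether any section closes the gap, and how many women it could concern.

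**1. Sections that could contain a second test**

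| Section | Content on this point | Closes the gap? |
|---|---|---|
| Exclusion Criteria, item 3 | Pregnancy, tied to the visit 1 urine test | No |
| Methods and Measures | Eligibility verified at visit 1; gap of at least 5 days | No |
| Study Visit 1 | Urine test before the IV dose | First dose only |
| Study Visit 2 | Fasting, vital signs, catheter, dose, sampling | No |
| Safety and Monitoring | Vital signs, symptom queries, nasal inspection | No |
| Long-term Follow-up | Daily contact for one week about adverse events | No, and it is not a pre-dose check |
| Inclusion Criteria, item 4 | Contraception or abstinence | Lowers the risk, detects nothing |

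The visit 2 procedures read as complete, so the absence does not look like a product of redaction or removed pages. A pregnancy present at visit 1 but too early for the urine test would also pass through, because nothing looks for it again.

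**2. Number of women concerned**

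Inputs: "We request permission to study up to 30 subjects" and a target of 24 evaluable (Sample Size); equal numbers of men and women, and three age groups of 18–39, 40–59 and 60–75 years (Methods and Measures). Equal age-group sizes are my assumption, since the plan does not give them.

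- Women enrolled, at most: 30 / 2 = 15
- Women among the evaluable: 24 / 2 = 12
- Women per age group: 30 / 3 / 2 = 5
- Women aged 18–39: 5
- Women aged 18–59: 2 × 5 = 10

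Roughly 5 to 10 women could therefore be of child-bearing potential, all of them required to use contraception. The documents give no pregnancy or contraceptive-failure rate, so I make no estimate of expected pregnancies.

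**3. Likely exposure at visit 2 relative to visit 1**

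Inputs: 102 µg intranasal, 14 µg intravenous, and the planning value in the Figure 3 legend: "The simulated model assumed a Cmax of 15 min and 1% bioavailability". The systemic amount is dose × bioavailability.

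- At 1%: 102 × 0.01 = 1.02 µg; 1.02 / 14 = 7% of the IV dose
- At 10% (my assumed upper case, not in the documents): 102 × 0.10 = 10.2 µg; 10.2 / 14 = 73% of the IV dose

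Exposure is below that of visit 1 in both cases. How far below is what the study sets out to measure.

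**4. Room for a lost subject**

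30 − 24 = 6 subjects may be lost, from all causes, before the evaluable target is missed.

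**The case against.** The strongest reply is that the plan already protects these women. Exclusion 3 bars pregnant women outright, so a known pregnancy stops the second dose. Inclusion 4 is written as a continuing condition: its one-cycle phrase sets a minimum lead time, not an end date, and visit 2 is also a study drug administration. On that reading contraception covers both doses. The remaining gap then needs a contraceptive failure, or a conception too early to detect at visit 1, and a pregnancy still unrecognised at visit 2. The number of women is small, the planning bioavailability implies low exposure, and the documents describe no specific harm from one intranasal dose in early pregnancy.

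Much of this stands. The risk is low, reading inclusion 4 as covering both doses is reasonable, and the 10% case is only an assumption. It does not remove the gap, because contraception and self-report do not detect an unrecognised pregnancy. The same contraception rule applies before visit 1, and the plan still tests there. A low assumed bioavailability is also a weak reason to omit the check in a study whose main objective is to determine bioavailability. The lack of documented harm limits how serious the point is, but the sponsor has already decided that pregnant women should not be dosed.

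**Conclusion.** The concern holds. Followed as written, the protocol could give the intranasal dose to a woman whose pregnancy is unrecognised, although its own exclusion is meant to prevent this. It is a minor participant-safety gap that should be closed because closing it costs so little. It concerns at most 15 women, and roughly 5 to 10 of child-bearing potential if the age groups are equal in size. The probability for any one woman is low but cannot be quantified from the documents. The conclusion itself rests only on the listed procedures, not on the bioavailability scenarios or the age split.

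**What to change.** Make two edits:

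1. In Study Visit 2, add a urine pregnancy test after arrival and before the intranasal dose for women of child-bearing potential. Visit 1 tests all female participants; applying the same rule at visit 2 would be equally acceptable.
2. In exclusion 3, change the parenthetical so that a positive urine test at visit 1 or visit 2 excludes the subject.

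With a test on the day of dosing, a maximum interval between visits is not needed for this purpose.

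The cost is about 5 to 10 extra urine tests, or at most 15 if every woman is tested. A positive result loses a subject after visit 1, which enrolment of up to 30 for 24 evaluable can absorb (6 spare, shared with all other losses). No analysis or sample-size figure changes.

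A separate, optional wording point: exclusion 1 names only the ingredients of Pitocin and could be extended to those of Tonix-1900. Hypersensitivity to oxytocin itself is already covered for both visits.
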